1.3 Number of patients

[figure not shown]
The primary objective of this study is to evaluate safety and tolerability of ceftaroline fosamil in neonates and young infants aged 7 to <60 days with LOS and the study is not powered for inferential statistical analysis. The sample size (24 patients; 3 cohorts of 8 patients) is considered adequate to evaluate the safety of ceftaroline fosamil in neonates and young infants with LOS.

2. ANALYSIS SETS

2.1 Definition of analysis sets

Figure 2 shows the relationship among different analysis sets graphically. The analysis of data will be based on different analysis sets according to the purpose of analysis, ie, for safety, efficacy, etc.

Figure 2 Study Analysis Sets

2.1.1 Intent-to-treat Analysis Set

The Intent-to-treat (ITT) Analysis Set will consist of all enrolled patients for whom informed consent form (ICF) was signed.

2.1.2 Safety Analysis Set

The Safety Analysis Set will be a subset of the ITT Analysis Set and will include all patients who received any amount of ceftaroline fosamil.

2.1.3 Modified Intent-to-Treat Analysis Set

The Modified Intent-to-treat (MITT) Analysis Set will include all patients who received any amount of ceftaroline fosamil and who met minimal disease criteria of LOS as described in the protocol inclusion criteria (diagnosis of sepsis within 36 hours before enrolment, defined as the presence of at least 2 clinical criteria and at least 1 laboratory criteria in the presence of or as a result of suspected or proven bacterial infection that requires IV antibiotic therapy). Patients with confirmed infection at baseline with a pathogen known to be resistant by CLSI methodologies and interpretive criteria (M100-S-28) to the study therapy received will be excluded. Patients with a confirmed fungal, parasitic, or viral pathogen as the sole cause of infection will also be excluded ([Appendix A](#)).

2.1.4 Microbiological Intent-to-Treat Analysis Set

The Microbiological Intent-to-treat (Micro-ITT) Analysis Set will include all ITT subjects who have one or more potentially causative baseline pathogens identified.

2.1.5 Pharmacokinetic (PK) Analysis Set

The PK Analysis Set will include all patients who received a known amount of ceftaroline fosamil, were randomized to a PK sample collection schedule, and had at least 1 PK sample collected.

2.2 Protocol deviations

Per PRA processes all important protocol deviations (PDs) as identified in the protocol deviation guidance document will be tracked and entered into the Clinical Trials Management System (CTMS). The study team will conduct ongoing reviews of PD data from CTMS throughout the study. Protocol deviations that the study team considers not to be important will not be tabulated or listed. Important protocol deviations will be verified as part of the final data review before database lock.

3. PRIMARY AND SECONDARY VARIABLES

For the calculation or derivations of the variables in this section, baseline will be defined as the last non-missing value before the start of study therapy. Change from baseline variables will be calculated for clinical laboratory tests and vital signs parameters as the post-treatment value minus the value at baseline. The visit windows for EOT, TOC, and SFU are defined in [Table 2](#) for efficacy analyses.

Study days are to be calculated starting from the onset of the first dose of study therapy, in 24-hour increments. If a date is prior to the first study therapy dose date (eg, date of LOS diagnosis, prior medication start date) then the study day will be calculated as (past date – first

study therapy dose date); if the assessment date is on or after the first study therapy dose date then the study day will be calculated as (assessment date – first study therapy dose date + 1). Durations in days will be calculated as (end date – start date +1).

Table 2 Visit Windows for EOT, TOC, and SFU

Visit	Protocol-defined Window
End of IV therapy (EOT)	Within 24 hours of completion of the last infusion of study drug
Test of cure (TOC)	8 to 15 days after the last dose of study drug
Safety follow-up (SFU)	28 to 35 days after the last dose of study drug

NB. Since there is no per protocol population defined for this study, scheduled visits will be used for MITT analyses and derived analysis windows will not be evaluated.

For analyses purposes, nominal visit data was used.

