4. STUDY PLAN AND TIMING OF PROCEDURES

Study Day 1 will start at the onset of study therapy and will end 24 hours later. Subsequent Study Days are to follow the same pattern. Any time reference to a Study Day within the protocol is to be calculated in reference to the given Study Day at the time of onset of the first dose of study therapy (eg, within 24 hours of Day 3 means the period starting 24 hours before Day 3 at the onset time of study therapy up to 24 hours after Day 3 at the onset time of study therapy).

Procedures will be performed according to the Study Plan located in [Table 1](#). The assessments and procedures should be conducted in person by the investigator or designee, unless otherwise indicated.

Results from any protocol-specified evaluations already performed locally as part of the patient's regular medical care can be recorded on the CRFs and do not have to be repeated for purposes of this study, as follows:

- Baseline clinical, laboratory, and microbiological tests: if performed within 36 hours of the first dose of study therapy
- Baseline chest radiograph (CXR), computed tomography (CT) scans, or other imaging tests: if performed as part of the patient's regular medical care within 72 hours of the first dose of study therapy
- After Baseline, any protocol-specified evaluations: if performed within 24 hours of any study day.

[Table 1](#) provides an overview of the protocol visits and procedures. Refer to the Study Assessments section of the protocol for detailed information on each procedure and assessment required for compliance with the protocol.

The investigator may schedule visits (unplanned visits) in addition to those listed on the schedule of activities table, in order to conduct evaluations or assessments required to protect the well-being of the subject.

Table 1 Study Plan detailing the procedures

Assessment or Procedure	Baseline ^a	Treatment period					Follow-up	
		Study Days*					EOT ^b	TOC ^c
		1	2	3	4-14			
Clinical	Written informed consent	X						
	Inclusion/exclusion criteria ^e	X						
	Medical history (including antepartum/peripartum period)	X						
	Adverse event review (AEs and SA Es)	X	X	X	X	X	X	X
	Prior and concomitant medications ^f	X	X	X	X	X	X	X
	Length	X						
	Weight	X	X	X	X	X	X	X
	Physical examination	X	X	X	X	X	X	
	Vital signs and oxygen saturation ^g	X	X	X	X	X	X	X
	Clinical outcome					X	X	
Laboratory	Record adjunctive therapeutic procedures (if performed)		X	X	X	X	X	X

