4.1. Baseline

Informed consent in writing will be obtained from parent(s) or legally-acceptable representative(s) before initiating any study assessment or procedure.

Baseline procedures must be completed within 36 hours before the start of the first dose of study therapy. If any such procedures have been carried out as standard-of-care within the timeframe they can be considered as baseline procedures. Potential patients who do not meet entrance criteria may, as appropriate, repeat Baseline evaluations at a later time for possible enrolment into the study.

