4.2.1. Study Day 1 (starts with onset of study drug administration)

Study Day 1 is the 24-hour period starting at the onset of the first administration of study therapy. Baseline assessments may be conducted within 36 hours before the onset of study therapy; therefore, Study Day 1 procedures described below are to be conducted within 24 hours of the onset of study therapy.

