8 June 2016	V2.0 Updated version of the SAP incorporating Protocol Amendment changes as outlined below: Change in definition of study day from “Study Day 1 is defined as the first day of study therapy administration.” to “Study Day 1 will start at the onset of study therapy and will end 24 hours later.”. Change in definition of cohort 2 from “Cohort 2: term neonates (defined as gestational age ≥38 weeks) aged 7 to ≤28 days ”. to “Cohort 2: term neonates (defined as gestational age ≥37 weeks) aged 7 to ≤28 days ”. Change in definition of cohort 3 from “Cohort 3: preterm neonates (defined as gestational age ≥34 to <38 weeks) aged 7 to ≤28 days ” to “Cohort 3: preterm neonates (defined as gestational age ≥34 to <37 weeks) aged 7 to ≤28 days ”. Change in dose from “Ceftaroline fosamil will be given at a dose of 4 mg/kg IV over 60 (± 10) minutes every 8 hours (q8h) (± 1 hour).” to “Ceftaroline fosamil will be given at a dose of 6 mg/kg IV over 60 (± 10) minutes every 8 hours (q8h) (± 1 hour).”. Change in requirements for administration of IV ampicillin and optional aminoglycoside from “IV ampicillin and optional aminoglycoside will be given as per standard of care.” to “IV ampicillin and optional aminoglycoside will be given as per standard of care. If the presence of an organism that requires treatment with ampicillin cannot be excluded, then the use of IV ampicillin for the first 48 hours is mandatory. If the result of additional microbiology, polymerase chain reaction or other investigations, indicate that ampicillin during the first 48 hours of treatment is not required, then its use is at the discretion of the investigator.”. In addition to the changes in relation to protocol amendments, additional tables were added for the duration of different Investigational Products (IP) [Ceftaroline, Ampicillin and Aminoglycoside]. Some additional programming notes were added to the shells to assist with the definition of variables within the derived/analysis datasets. An additional appendix was added to the SAP to list the criteria for potentially clinically significant laboratory tests. An additional appendix was added to the SAP to indicate the TFLs required for the Data Safety Monitoring Board (DSMB).

Date	Brief description of change
12 July 2016	V2.1 Updated to incorporate client review comments on V2.0. Updated to incorporate protocol amendment 2 changes: study medication dose changed from 4mg/kg to 6mg/kg.

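### Does deriving study day from calendar dates, when the SAP defines it in 24-hour blocks, require a change to the plan?

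*SAP*

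**What the plan says.** SAP Section 3 gives the definition first: "Study days are to be calculated starting from the onset of the first dose of study therapy, in 24-hour increments". This matches Protocol Section 4 ("Study Day 1 will start at the onset of study therapy and will end 24 hours later") and Protocol 4.2.1 ("Study Day 1 is the 24-hour period starting at the onset of the first administration of study therapy"). The next sentence of SAP Section 3 gives a formula in dates. A date before the first-dose date takes the plain difference. For a date on or after it, "then the study day will be calculated as (assessment date – first study therapy dose date + 1". Clock time plays no part.

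The same section sets the general convention for lengths of time: "Durations in days will be calculated as (end date – start date +1". SAP 3.3.3 applies it to exposure (last therapy date minus first, plus one day). SAP 4.2.5 tabulates exposure for ceftaroline fosamil, ampicillin and aminoglycoside, and adds a figure for total treatment days that it does not define separately.

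On visits, the note under the window table in SAP Section 3 says: "For analyses purposes, nominal visit data was used".

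**The concern.** Two adjacent sentences state different rules, and the 24-hour rule looks deliberate. The SAP amendment history for V2.0 records a "Change in definition of study day from" the first day of administration to the 24-hour period. The formula seems not to have been brought into line. Pre-dose records on the first-dose date are to be expected, since "Baseline procedures must be completed within 36 hours before the start of the first dose of study therapy", and the formula labels them Day 1 although no drug has been given.

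Exposure raises a second worry. Protocol 7.2.3 lets the aminoglycoside be stopped and restarted, and Protocol 7.2.4 foresees missed or postponed dosing if renal function worsens. A first-to-last span then includes days without drug, and the tables might present these as treatment days. Safety is the primary objective and only 24 patients are planned, so listings will be read patient by patient. A wrong day label or an inflated exposure could mislead such a reader.

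**Working it through.** The plan states no figure to reproduce, so the check compares the two rules and then asks which outputs use the result.

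**1. Size of the labelling difference.** Let the first dose be at clock hour *u*. Each 24-hour study day runs from *u* to *u* on the next date. Its last *u* hours fall on the later date and are labelled one day too high. With assessment times uniform over the clock (an assumption; the documents give no distribution), the share affected is *u*/24:

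- 02:00 start: 2/24 = 8%
- 08:00 start: 8/24 = 33%
- 14:00 start: 14/24 = 58%
- 20:00 start: 20/24 = 83%
- average over uniform starts: 12/24 = 50%

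The difference is always 0 or +1. With a first dose at 20:00 on 1 June, an assessment at 08:00 on 2 June (12 hours later) is Day 2 by formula and Day 1 by definition.

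**2. Pre-dose records.** The baseline window is 36 hours, of which *u* hours lie on the first-dose date. The share labelled Day 1 is *u*/36: 8/36 = 22%, 14/36 = 39% and 20/36 = 56% for starts at 08:00, 14:00 and 20:00.

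**3. Where the derived day is used.**

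- Baseline is the last non-missing value before therapy starts (SAP 3). It does not use the day number.
- Treatment emergence is set by the start of administration (SAP 3.1.1.1 and 4.2.6.1).
- By-visit summaries use nominal visits, and SAP 3 says that derived windows will not be evaluated.
- The EOT, TOC and SFU windows count from the last infusion or last dose, not from Day 1.
- Clinical response comes from the investigator's assessment, and its 48-hour threshold is in hours (SAP 3.2.1.1).
- The study days that the SAP names are for diagnosis and prior-medication dates (SAP 3) and for procedure and condition start dates (SAP 3.3.1.2). For date-only items, a date formula is the right tool.

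**4. Exposure, complete course.** The last of *k* eight-hourly infusions starts 8(*k* − 1) hours after the first. On calendar dates the span is floor((*u* + 8(*k* − 1))/24) + 1.

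- *k* = 42: 328 hours, so 14 days if *u* < 8 and 15 otherwise. On date-times, 328/24 + 1 = 14.67.
- *k* = 6: 40 hours, so 2 days if *u* < 8 and 3 otherwise. On date-times, 40/24 + 1 = 2.67.

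The calendar convention therefore adds at most one day to an uninterrupted course.

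**5. Exposure, gaps.** For ceftaroline, assume 42 expected infusions with the first and last given. Three missed give 39/42 = 92.9% compliance, eight give 34/42 = 81.0%, and nine give 33/42 = 78.6%. Up to eight missed stay in the 80–120% category, but the continuous compliance summary shows them, and SAP 4.2.5 lists administration details by patient. For an aminoglycoside given on dates 1–3 and 10–12, the span is 12 − 1 + 1 = 12 days, against 6 dosed dates.

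**6. Would infusions divided by three be a better count?** No. Three infusions missed on three different days leave drug given on all 14 days, yet 39/3 = 13. Eight missed on eight different days also leave 14 treated days, yet 34/3 = 11.3. That quotient measures dose-equivalents, not days treated.

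**The case for a change.** The best case for a change is that the SAP contradicts itself in consecutive sentences, that a programmer has to choose, and that alignment costs a line of wording and a simple derivation. Infusion dates and times are already recorded (Protocol 7.5). That a date formula is common practice is no answer when the sentence before it states another rule. The contradiction stands, as does the mislabelling of timed records in any listing that shows a derived day. The table shells are not among the documents, so such listings cannot be ruled out.

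The supposed harm, that one assessment carries a nominal day and a different derived day, would nevertheless survive alignment. Protocol Section 4 accepts local post-baseline results obtained within 24 hours of a study day, and its Day 3 example reaches back 24 hours. A nominal Day 3 result can thus lie in the Day 2 block even under a strict 24-hour derivation. Alignment would also put two scales under one name, elapsed blocks for timed records and calendar days for date-only ones.

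On exposure, it is fair that aminoglycoside gaps are less visible: SAP 4.2.5 promises administration details for ceftaroline only, although SAP 4.1 says that all data will be listed. But SAP 3.3.3 states the span formula openly, and that total treatment days is the sum of these spans is an inference. The option to miss or postpone ceftaroline doses is tied to worsening renal function, and the same section expects no renal dose adjustment.

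**Conclusion.** The inconsistency in SAP Section 3 is real but editorial. The derived study day of a timed record can be 0 or 1 day too high, and a pre-dose record on the first-dose date is labelled Day 1. The shares above (8% to 83% after dosing, 22% to 56% of the baseline window) rest on assumed clock times and describe labels, not results. Adverse event incidence, treatment-emergent status, change from baseline, nominal-visit summaries and clinical response are the same under either rule, so a change would bring no identified gain. Analysts can read the 24-hour rule as governing timed records and the date formula as serving date-only items.

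The exposure span is an ordinary, stated convention for a descriptive table. It can exceed treated time by up to a day for an uninterrupted ceftaroline course, and by the length of any gap otherwise. Compliance and the administration listing show ceftaroline gaps. A table footnote saying that the figure is a first-to-last span would be good practice, but the plan need not change for it. This conclusion assumes that the unseen table shells do not use the derived study day to select or group timed records; nothing in the SAP suggests that they do.

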3.1 Primary outcome variables

3.1.1 Safety variables

The safety analysis will be performed using the Safety Analysis Set. Safety parameters include AEs, serious adverse events (SAEs), deaths, clinical laboratory parameters (eg, complete blood count [CBC] with differential, chemistry panel), and vital signs.

No imputation on missing data will be undertaken for safety parameters.

3.1.1.1 Adverse events (AE) variables

An AE is the development of any new undesirable medical condition or the deterioration of a pre-existing medical condition following or during exposure to a pharmaceutical product, whether or not considered causally related to the product. An undesirable medical condition can be symptoms (eg, nausea, chest pain), signs (eg, tachycardia, enlarged liver), or the abnormal results of an investigation (eg, laboratory findings). In clinical studies, an AE can include an undesirable medical condition occurring at any time, even if no study therapy has been administered. All AEs will be classified using the Medical Dictionary for Regulatory Activities (MedDRA) version 12.0 or higher.

The term AE is used to include both serious and nonserious AEs. Each AE will be graded for intensity (mild, moderate, severe). If intensity is missing it will be presented as such in the corresponding Tables. Each AE will be assessed for relationship to the study therapy (yes, no) as well. If relationship to study therapy is missing it will be presented as such in the corresponding Tables.

Adverse events will be collected from the time the parent(s)/legal guardian/legally acceptable representative provides informed consent throughout the treatment period up to and including the SFU visit in the study. AEs occurring after the start of administration of the first dose of study therapy or AEs that started prior to treatment and worsened on treatment up to and including the SFU visit will be summarised.

Adverse events of special interest (AESI) will be selected by subsetting MedDRA preferred terms from Pseudomembranous colitis Standard MedDRA Query (SMQ narrow), Anaphylactic reaction (SMQ narrow), Angioedema (SMQ narrow), and Malignancies (SMQ

narrow). The MedDRA preferred terms identifying the AESI were provided by Pfizer, see [Appendix C](#).

Serious adverse events variables

A SAE is an AE occurring during any study phase (ie, treatment, follow-up), that fulfils one or more of the following criteria:

- Results in death
- Is immediately life threatening
- Requires inpatient hospitalization or prolongation of existing hospitalization
- Results in persistent or significant disability or incapacity
- Is a congenital abnormality or birth defect
- Is an important medical event that may jeopardize the patient or may require medical intervention to prevent one of the outcomes listed above
- Is any suspected transmission via a medicinal product of an infectious agent.

SAEs will be collected from baseline throughout the treatment period up to and including the SFU visit in the study. SAEs occurring in a subject after the active collection period has ended are reported to Pfizer Safety if the investigator becomes aware of them; at a minimum, all SAEs that the investigator believes have at least a reasonable possibility of being related to investigational product must be reported to Pfizer Safety. SAEs reported after the active collection period will be reported in the Pfizer Safety database only, not in the clinical database.

Analysis of SAEs will focus on treatment-emergent SAEs which will be those occurring after the start of administration of the first dose of study therapy or SAEs that started prior to treatment and worsened on treatment.

3.1.1.2 Death

For any patients who die during the study, date and time of death, autopsy yes/no, and primary and secondary cause of death will be collected.

3.1.1.3 Clinical laboratory variables

The safety laboratory parameters presented in [Table 3](#) will be measured.

Table 3 Laboratory safety variables

Chemistry panel	CBC and differential	Urinalysis
Albumin	Haematocrit	Bilirubin
Alkaline phosphatase	Haemoglobin	Blood
Alanine aminotransferase	Red Blood Cell count	Glucose
Aspartate aminotransferase	White Blood Cell count	Protein
Bilirubin, total and direct	Eosinophils ^c	pH
Blood urea nitrogen	Lymphocytes ^c	Specific Gravity
Urea	Monocytes ^c	Colour
Calcium	Neutrophils ^c	Appearance
Chloride	Platelets	Nitrite
Creatinine ^a	Immature granulocytes ^c	Urobilinogen
Glucose, nonfasting ^a	Metamyelocytes ^c	Leukocyte esterase
Potassium	Myelocytes ^c	
Sodium	Promyelocytes ^c	
Bicarbonate (HCO ₃) ^b	Blasts ^c	
Lactate Dehydrogenase ^b		
pH ^b		
C-reactive protein ^b		
Procalcitonin ^b		

^a Required for eligibility.

^b Test not mandatory for eligibility if other eligibility criteria are met.

^c Absolute count and/or %.

Hematology and chemistry will be performed at every visit or as clinically indicated. Urinalysis, 8-hour urine output if available, and CSF samples will be collected through the TOC visit. If available, base excess (BE) will be calculated from blood gases, and C-reactive protein (CRP) and procalcitonin will be assessed during the treatment period only.

Système International units will be reported for all analytes. Local laboratory upper limit of the normal range (ULN) and lower limit of the normal range (LLN) values for laboratory parameters will be applied for safety data in this study. No ULN or LLN are defined for vital signs parameters in the pediatric setting. Selected potentially clinically significant (PCS) laboratory results will be defined; see [Appendix B](#) for a list of PCS laboratory results.

